10. STATISTICAL ASPECTS

Study size calculation

Considering the results of the performance verification tests of the medical device under study, we have established the study hypotheses in connection with the calculation of the size of the study set out below:

Minimum acceptable value of the ICC correlation coefficient (ρ_0)	0.6
Expected value of the ICC correlation coefficient (ρ_1)	0.7
The number of observations per subject k	3
Two-sided significance level (α)	0.05
Power (1 - β):	90%
Minimum size (n)	226
Size at 30% safety margin	323

A final study size of 323 patients is retained; taking into account a rate of unusable data of 30% in order to maintain the statistical power of the study in the event of exclusion of outliers.

Statistical methods used

The analysis will carry an initial descriptive part. The qualitative variables will be expressed in frequencies (with their 95% CI), and the quantitative variables expressed in means (with their standard deviation) if the distribution is normal. Otherwise, the quantitative variables will be expressed as the median (with their interquartile range).

Then, we will perform a comparative analysis, using chi 2 tests (or Fisher's exact) for the qualitative variables and student test (or Mann-Whitney test if applicable) for the quantitative variables. For performance estimation, we will determine the intra-class correlation coefficient with its confidence interval and we will perform a graphical analysis of Bland and Altman. In addition, we will calculate the mean square errors between the measurement with COBOX and the reference measurements, and they will be expressed as a percentage.

All our analyzes will be carried out at the 5% significance level.

An analysis of the repeated and compared measurements between COBOX and the CE marked device (used during the technical reference process for taking measurements) for the heart rate will make it possible to evaluate the reproducibility of the COBOX on repeated measurements in the *COBOX Protocol Valid*

same individual. A secondary statistical analysis will be done for the measurement times T+5s and T+10s.

We will use imputation methods or sensitivity analysis for the management of missing data.

11. Access rights to source data and documents

Access to data

The sponsor is responsible for obtaining the agreement of all the parties involved in the clinical investigation in order to guarantee direct access to all the places where the research is carried out, to the source data, to the source documents and to the reports in a purpose of quality control and audit by the Sponsor.

The investigators will make available the documents and individual data strictly necessary for the monitoring, quality control, audit of the clinical investigation and available to persons having access to these documents in accordance with the legislative and regulatory provisions in force (articles L.1121-3 and R.5121-13 of the public health code).

Source data

Any original document or object that proves the existence or accuracy of data or a fact recorded during the research is defined as a source document.

List the type of source document as part of the research (medical record, original biological examination result, imaging examination report, etc.).

Data Privacy

In accordance with the legislative provisions in force (articles L.1121-3 and R.5121-13 of the Public Health Code), persons having direct access to the source data will take all the necessary precautions to ensure the confidentiality of the information relating to the research, to the persons who take part in it and in particular with regard to their identity as well as to the results obtained. These people, like the investigators themselves, are subject to professional secrecy.

During the clinical investigation or at its end, the data collected on the people who agree to it and transmitted to the sponsor by the investigators (or any other specialized contributors) will be made anonymous. Under no circumstances should they clearly show the names of the persons concerned or their addresses.

The Sponsor will ensure that each person who lends himself to the research has given his written consent for access to the individual data concerning him and strictly necessary for the quality control of the research.

12. Quality control and assurance

Guidelines for data collection

All the information required by the protocol must be recorded in the tablet in the boxes dedicated to this purpose. Data should be collected as it is obtained.

Research follow-up

The clinical investigation will be monitored by a clinical research technician. He will be responsible, alongside the coordinating investigator, for:

- Research logistics and monitoring,
- Reporting on its progress,
- Verification of data collection with the tablet,
- The transmission of SAEs to the Sponsor.

He will work in accordance with standard operating procedures, in collaboration with the clinical research associate delegated by the Sponsor.

Quality control

A clinical research associate mandated by the sponsor visits each investigating center on a regular basis, during the setting up of the research, one or more times during the research depending on the rate of inclusions and at the end of the research. During these visits, the following elements will be reviewed:

- informed consent,
- Compliance with the research protocol and the procedures defined therein,
- Quality of data collected in the tablet: accuracy, consistency of data with source documents (medical records, appointment books, original laboratory results, etc.).

Any visit will be the subject of a monitoring report in written form.

Data management

Data processing will be carried out under the responsibility of [name].

The data will be entered automatically and stored in the tablet reserved for the study and provided by the sponsor.

The data validation and freezing processes will be carried out according to the procedures in force.

Auditing and inspection

An audit may be carried out at any time by persons appointed by the Sponsor and independent of the research managers. Its objective is to ensure the quality of research, the validity of its results and compliance with the law and regulations in force.

Investigators agree to comply with the requirements of the sponsor and the competent authority with respect to an audit or inspection of the research.

The audit may apply to all stages of the research: from the development of the protocol to the publication of the results and the classification of the data used or produced within the framework of the research.

13. Ethical and Regulatory Considerations

The sponsor and the investigator(s) agree that this research will be carried out in accordance with the Public Health Code, as well as in accordance with Good Clinical Practice (ICH version 4 of May ¹ 1996 and decision of November 24, 2006) and the Declaration of Helsinki (which can be found in its integral version on the site <http://www.wma.net>) and according to the MDR 745/2017. The research is conducted in accordance with this protocol. Except in emergency situations requiring the implementation of specific therapeutic acts, the investigator(s) undertake(s) to respect the protocol in all respects, in particular with regard to the collection of consent.

This research received an ID-RCB number on the ANSM website: <https://ictaxercb.ansm.sante.fr/Public/index.php>.

Assurance QUANTIQ – Sponsor of the study

As part of this research, subject to Law No. 2018-493 of June 20, 2018 on the protection of personal data, the data recorded during this research is subject to computerized processing by Quantiq. io in order to analyze the results of the research with regard to the objectives of the latter. In accordance with the General Data Protection Regulation (RGPD 2016/679 of the European Parliament and of the Council of April 27, 2016), health data will be processed for scientific research purposes in compliance with the fundamental rights and interests of the person. suitable for research (Article 9 §2, paragraph i and j).

The data controller for this study is [name].

People participating in the research have a right of access to their data, a right of rectification, erasure of their data, a right to limit processing as well as a right of opposition. to the processing of their personal data. These rights are exercised with the Investigator, who will inform the sponsor of the research as soon as possible.

People taking part in the research also have the right to lodge a complaint with the supervisory authority in France, namely the Commission Nationale de l'Informatique et des Libertés (CNIL).

The personal data will only be accessible to the persons concerned (those participating in this research) and to the persons charged by the sponsor with controlling the quality of the study. These data will be pseudonymised: they will be marked by a code number comprising an inclusion number (corresponding to the chronological order of their inclusion and the center number) as well as the 1st letter of the name and the 1st letter of the first name of each concerned person. The correspondence table will be kept separately from the entire data set by the only persons authorized by the Sponsor, who will not be data operators. If necessary, they may also be transmitted to the authorized health authorities, under the legal conditions provided. In all cases, they will be used under conditions guaranteeing their confidentiality.

This data processing may be part of the reference methodology MR001 according to article 62.1 of the MDR.

For comfort, the company Quantiq.io filed a request for CNIL authorization on December 24, 2021, supported by a PIA.

Protocol amendment

Changes to the protocol will be managed in accordance with the requirements of Regulation 2017/745.

Any substantial modification, i.e. any modification likely to have a significant impact on the protection of persons, on the conditions of validity and on the results of the research, on the quality and safety of the products tested, on the interpretation of the scientific documents that support the progress of the research or the methods of conducting it, is the subject of a written amendment which is submitted to the sponsor; the latter must obtain, prior to its implementation, a favorable opinion from the CPP and inform the ANSM.

Non-substantial modifications, ie those having no significant impact on any aspect of the research whatsoever, are communicated to the CPP for information.

All amendments are validated by the sponsor, and by all the research stakeholders concerned by the modification, before submission to the CPP.

All amendments to the protocol must be brought to the attention of all investigators participating in the research. Investigators undertake to respect its content.

Any amendment that modifies the care of patients or the benefits, risks and constraints of research is the subject of a new information note and a new consent form, the collection of which follows the same procedure as the one mentioned above. .

Deviation from protocol

Any deviation from this protocol, the signed agreement, applicable regulations and any condition of approval imposed by an EC or by applicable regulatory authorities, which affects the rights, safety and well-being of the subjects or the scientific integrity of the clinical investigation, must be documented (including the date and reason for the deviation). Site staff must identify and report deviations to the sponsor within 5 working days.

In emergency circumstances, deviations from this protocol to protect the rights, safety, or well-being of participants are permitted without the prior approval of the sponsor and investigators. The site must document and report these emerging deviations to [name] and [name] and to the EC within 5 working days of the occurrence of the emergency.

Where appropriate, measures to ensure compliance may be taken by the data controller. These actions may include discontinuation of device shipments, removal/disposal of devices from the investigator, or termination of the investigator's participation in the study.

Declaration of conformity

- A) This clinical investigation will be conducted in accordance with the ethical principles which have their origin in the Declaration of Helsinki, the ISO 14155:2020 standard (Clinical investigation of medical devices for human subjects - Good clinical practice).
- B) This clinical investigation will be conducted in accordance with this International Standard and any regional or national regulations, where applicable, including Regulation 2017/745.
- C) This clinical investigation will not commence until the required approval/favourable opinion has been obtained from the EC or the regulatory authority, as the case may be.
- D) Any additional requirements imposed by the EC or regulatory authority will be followed, as applicable.

14. Preservation of documents and data relating to research

The following documents relating to this research are archived in accordance with Good Clinical Practice:

– By the medical investigators:

- for a period of 15 years (research relating to drugs, medical devices or in vitro diagnostic medical devices or research not relating to a product mentioned in Article L.5311-1 of the Public Health Code),
 - The protocol and any amendments to the protocol
 - Observation notebooks (copies)
 - The electronically signed informed consents of the participants
 - The source files of the participants who signed a consent
 - All other documents and letters relating to the research

All these documents are the responsibility of the investigator for the regulatory archiving period.

– By the Sponsor:

- for a period of 15 years (research relating to drugs, medical devices or in vitro diagnostic medical devices or research not relating to a product mentioned in Article L.5311-1 of the Public Health Code),
 - The protocol and any amendments to the protocol
 - The original observation notebooks
 - A copy of the electronically signed informed consents of the participants
 - Documents relating to serious adverse events
 - All other documents and letters relating to the research

All these documents are under the responsibility of the Sponsor for the regulatory archiving period. No displacement or destruction can be carried out without the agreement of the Sponsor. At the end of the regulatory archiving period, the Sponsor will be consulted for destruction. All data, documents and reports are subject to audit or inspection.

15. Posting Rules

Scientific papers

The data provided by the investigating centers are centralized by the coordinating center and sent to Quantiq.io for statistical analysis (statistical analysis is done by Quantiq.io). This analysis gives rise to a written report which must then be sent to the Committee for the Protection of Persons and to the competent authority.

Any written or oral communication of the results of the research must receive the prior agreement of the coordinating investigator and, where applicable, of any committee set up for the research.

The publication of the main results mentions the name of the sponsor, of all the investigators who included or followed patients in the research, of the methodologists, biostatisticians and data managers who participated in the research, of the members of the committee(s) set up(s) for research and funding source(s). International rules for writing and publication will be taken into account (The Uniform Requirements for Manuscripts of the ICMJE, April 2010).

Communication of results to patients

In accordance with law n°2002-303 of March 4, 2002, patients are informed, at their request, of the overall results of the research.

Transfer of data

Data collection and management are handled by the coordinating centre. The conditions for the transfer of all or part of the research database are decided by the research sponsor and are the subject of a written contract.

Sponsor		COORDINATING INVESTIGATOR	

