COBOX is a tool for measuring cardiac and respiratory rhythm in routine clinical practice for patients outside intensive care and outside continuous monitoring. We expect a correlation coefficient of more than 0.7 between the COBOX measurements and those obtained using the reference method. Regarding the secondary endpoints, we expect average standard deviations

between COBOX and the reference methods of 5 bpm for the heart rate and 3 bpm for the respiratory rate.

Expected benefits

These data will validate the COBOX tool in terms of measurement performance compared to the results obtained through the application of reference processes for taking measurements using CE marked devices, as well as those obtained using the reference method of counting manual. Applications for taking physiological constants without contact have a wide field of application in the field of routine care and save medical time, increase quality by limiting manual copying errors and the risk of contamination.

6. Research design

Research scheme

This is an observational study, responding to Article 62.1 of the European medical device regulations, prospective, comparative.

Primary endpoint

The main judgment criterion will be the intra-class correlation coefficient between the measurement by COBOX and the measurement obtained thanks to the application of the reference processes for taking measurements via a measurement by a CE marked tool (for HR).

In order to ensure the repeatability of the device, three successive comparative measurements (each spaced 5 seconds apart) on the same patient will be carried out.

Secondary endpoints

The additional secondary judgment criteria will be:

- For RF (ranked criterion): comparison with a manual measurement following a reference method of manual counting according to good training practices for healthcare personnel trained in taking measurements (ide, as, internal external).
- The reliability of the reproducibility of the measurement
- The time in seconds dedicated to taking the parameters with and without the COBOX tool (time for installing and removing the tool if applicable, time for completing the medical file if applicable, effective time for taking the HR constants and FR).
- Assessment of treatment costs:
 - Pick-up times / delays
 - Total treatment costs (direct medical and non-medical costs)

Inclusion criteria

- Adult patient (18 years and over)
AND
- Patient consulting in the emergency department of a participating center
AND

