- Patient having constant FC and FR taken by the nursing staff (or arc or tec) of emergency reception
AND
- Patient who did not express his opposition to participate in the study
AND

- Patient affiliated to a social security scheme

Non-inclusion criteria

- Patient in a state of vital emergency with direct entry into SAUV or intensive care.
- Patient unable to express consent.
- Patient unable, for health reasons, to face the COBOX tool.
- Patient unable to stand for 30 seconds facing the COBOX solution.
- Patient with skin stigma over more than 50% of the face (burn, graft)
- Patient with the face covered or not allowing access to the entire face (clothing)

Recruitment methods

In order not to delay the care of patients in the emergency room, recruitment is carried out by the IOA (or arc or tec) at the time of their usual care. She communicates oral information to the patient on the use of the tool during the measurements and presents the consent letter in electronic format in the tablet. If the patient gives consent, the test is performed. In case of opposition, the COBOX device will not be used.

It is therefore a serial recruitment, without selection of the participants.

7. Experimental device(s) and comparator(s)

Description of exposure to comparators

In order to standardize the measurements of the four hospital centers, QUANTIQ will provide each center with a CMS60D digital pulse oximeter from the Contec brand. This device is CE marked and commonly used in hospitals. This device will be used at the same time as the CE marked device used during the reference technical process of the hospital center, without modifying the practices of each center. The comparison of results will be between the Contec CMS60D and the COBOX tool.

Device	Acquisition cost	Trolley (300 to 700 Euros)	Whip Set and Monobase Cables	Lifespan (Year)	Annual Maintenance Cost	Annual cost for 1 technical platform
Contec CMS60D Digital Pulse Oximeter (SpO2 - Heart Rate)	242.50 €	N / A	N / A	2 YEARS (AVERAGE)	Replaced/No Maintenance - PURCHASE Management (12.1 €)	133.4 €

List of any other medical device or drug that will be used during the clinical investigation.

The Contec CMS60D reference DM will be provided by Quantiq while COBOX will be installed on a Samsung S6 tablet also provided by Quantiq.

Number of experimental devices to be used, along with a rationale

3 reference Contec CMS60D oximeters will be provided per center.

Treatment(s)/ management of experimental devices

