
QUANTIQ provides users with one tablet per site per physician. Delivery of a functional tablet in the event of a malfunction within 5 working days. Bug fix within 3 days in case of software malfunction with continuous information for professionals.

8. Research process

Research timeline

- Start of inclusions: Mid-July 2022
- Duration of the inclusion period: 2 months
- Duration of participation of each patient: The time of their passage in the IOA box (less than 30 minutes)
- Total research duration: 3 months

Summary of patient follow-up

- Oral information by the IOA. If necessary, an investigating physician can complete the information at the patient's request.
- Informed consent with electronic signature.
- Collection of the patient's age, gender and Fitzpatrick phototype.
- Collection of patient identification number.
- The nursing staff (or arc or tec) installs the oximeter on the patient's finger.
- The nursing staff (or arc or tec) starts COBOX and begins to count the breaths in parallel.
- After 15s, a first measurement is made by COBOX. The pulse oximeter reference result is acquired in parallel, associated with the patient ID number and stored with the COBOX result at the same time on an electronic database.
- After 20s (5s after the previous measurement), a second measurement is made by COBOX. The pulse oximeter reference result is acquired in parallel, associated with the patient ID number and stored with the COBOX result at the same time on an electronic database.
- After 25s (5s after the previous measurement), a third measurement is made by COBOX. The pulse oximeter reference result is acquired in parallel, associated with the patient ID number and stored with the COBOX result at the same time on an electronic database.
- After 30s, the nursing staff (or arc or tec) enters the number of breaths counted since the start. This result is converted into a respiratory rate (RR) then associated with the patient number and stored in the database.

The data is blocked on the database until the end of the study. At the end of the study, they will be sent to the coordinating centre.

In order not to disrupt the general operation of the emergency department and patient care, the usual patient circuit is not modified. The COBOX tool is used by the reception staff in a contemporary way to their usual collection of input parameters.

Collection of consent

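### The sample size assumes three interchangeable readings per patient, but the primary ICC compares two devices, so 90% power at 226 is not established (about 74% for one pair per patient)

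*Combined protocol and SAP*

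**What the plan says.** - **Sample size (section 10, Study size calculation).** Minimum acceptable ICC 0.6, expected ICC 0.7, two-sided alpha 0.05, power 90%, and 3 for "The number of observations per subject k". The result is 226, raised to 323 for 30% unusable data.
- **Primary endpoint (section 6).** "The main judgment criterion will be the intra-class correlation coefficient between the measurement by COBOX and the measurement obtained" with the CE-marked reference, for heart rate. The same subsection adds: "In order to ensure the repeatability of the device, three successive comparative measurements", spaced 5 seconds apart.
- **Comparator (section 7).** "The comparison of results will be between the Contec CMS60D and the COBOX tool".
- **Procedure (section 8, Summary of patient follow-up).** COBOX reads at 15, 20 and 25 s. Each time, "The pulse oximeter reference result is acquired in parallel". Each patient therefore gives three simultaneous pairs, six readings in all.
- **Analysis (section 10, Statistical methods used).** An ICC with a confidence interval is planned, without naming its form or the readings used. "An analysis of the repeated and compared measurements between COBOX and the CE marked device" is to assess reproducibility. Then: "A secondary statistical analysis will be done for the measurement times T+5s and T+10s". T is not defined.
- **Expected performance (section 5).** "We expect a correlation coefficient of more than 0.7 between the COBOX measurements and those obtained using the reference method".

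**The concern.** In the ICC sample-size formula, k is the number of interchangeable readings per patient that enter the coefficient. Three would suit an ICC among the three COBOX repeats, which is a repeatability measure and not the primary endpoint. The primary ICC sets one device against another, so a single pair per patient means k = 2. Three pairs per patient are six readings in which simultaneous readings share the patient's heart rate at that moment and each device's errors may carry over between repeats. That structure is not three interchangeable readings either.

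The 90% power is the stated justification for 226 and 323. If it was derived for another coefficient, the chance of showing agreement above the plan's own minimum is unknown and could be well below what is stated. The readings and the ICC form are also left open, and the sponsor runs the analysis itself (section 15, Scientific papers), so nothing in the plan prevents these choices from being made after the data are released.

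**Working it through.** **Inputs (section 10 table):** ρ0 = 0.6, ρ1 = 0.7, k = 3, two-sided α = 0.05 (z = 1.960), power 90% (z = 1.282), 30% unusable.

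**1. Reproduce the plan's figures.** The standard formula for testing an ICC is

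n = 1 + 2(zα + zβ)² k / [(k − 1)(ln C0)²], with C0 = [1 + kρ0/(1 − ρ0)] / [1 + kρ1/(1 − ρ1)].

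- (zα + zβ)² = 10.507.
- k = 3: C0 = (1 + 3 × 1.5)/(1 + 3 × 2.3333) = 5.5/8 = 0.6875 and (ln C0)² = 0.1404. So n = 1 + 2 × 10.507 × 3/(2 × 0.1404) = 225.5, rounded up to 226.
- 226/0.70 = 322.9, rounded up to 323.

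Both stated figures reproduce. Other variants do not give 226: k = 3 one-sided gives 184, k = 3 at 80% power 169, k = 2 two-sided 348, k = 2 one-sided 284, k = 6 two-sided 155.

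**2. One pair per patient (k = 2).** C0 = (1 + 2 × 1.5)/(1 + 2 × 2.3333) = 4/5.6667 = 0.7059 and (ln C0)² = 0.1213. So n = 1 + 2 × 10.507 × 2/0.1213 = 347.4, rounded up to 348.

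Exact power is P(F > C0 × F0.975), with n − 1 and n(k − 1) degrees of freedom:

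| Evaluable | Loss from 323 | Power, k = 2, true ICC 0.70 |
|---|---|---|
| 226 | 30% | 74.2% |
| 258 | 20% | 79.7% |
| 291 | 10% | 84.2% |
| 323 | none | 87.8% |
| 348 | – | 90.0% |

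For comparison, k = 3 at 226 gives 90.2%. At an observed ICC of 0.70 with 226 patients, the 95% interval is 0.627 to 0.761 for k = 2 and 0.643 to 0.752 for k = 3.

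**3. Sensitivity to the true ICC (k = 2, n = 226).** Power is 82.8% at 0.71, 89.5% at 0.72, 94.2% at 0.73 and 98.7% at 0.75. It reaches 90% at about 0.721 with 226 patients and about 0.703 with 323.

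**4. All three pairs pooled.** Power now depends on the correlation of a device's errors between repeats and on how much of the variance shared by the two devices is patient-by-time. The plan gives neither, so both are assumed. Simulation used components for patient, patient-by-time, patient-by-device and residual, a same-time between-device ICC of 0.6 against 0.7, and the upper 2.5% critical value under 0.6:

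| Evaluable | Patient-by-time share | Error correlation 0 | 0.5 | 0.9 | 1 |
|---|---|---|---|---|---|
| 226 | 0% | 95% | 89% | 78% | 74% |
| 226 | 10% | 96% | 91% | 80% | 76% |
| 226 | 20% | 97% | 92% | 82% | 78% |
| 323 | 0% | 99% | 97% | 90% | 88% |
| 323 | 10% | 99% | 97% | 92% | 89% |
| 323 | 20% | 99% | 98% | 93% | 91% |

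At 226, 90% is met only up to an error correlation of about 0.4 to 0.6. A check on simulated raw data with a patient-clustered interval and no known components gave 94/88/78/75% (0% share) and 97/93/83/78% (20% share), with one-sided error of 2.3 to 2.8%.

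**5. Mean of three readings per device.** The documents do not mention this option, but they do not exclude it. With a single-reading ICC of 0.7, no drift and the threshold kept at 0.6, averaging at error correlation 0.9 reduces the error share from 0.3 to 0.3 × (1 + 2 × 0.9)/3 = 0.28. The ICC becomes 0.7/0.98 = 0.714 and power at 226 is about 86%. At correlation 1 it is 74%; at 0.5 or below it is above 99.9%.

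**The case against.** - **The arithmetic is right.** This stands: 226 and 323 follow from the table's inputs. The fault is that the inputs describe a different coefficient from the primary one.
- **Three observations are collected per patient, so k = 3 is natural.** This does not stand. Six readings are collected in three simultaneous pairs, and neither one pair nor three pairs amounts to three interchangeable readings.
- **The plan may intend all three pairs, and power could then exceed 90%.** This partly stands. Section 6 places the three comparative measurements under the primary endpoint, and with weakly correlated errors the target is met. However, section 10 makes T+5s and T+10s secondary. If T is the first reading, these are the 20 s and 25 s readings, which favours one pair and the 74% figure. The 97% upper end also needs zero error correlation and an assumed 20% patient-by-time share; with no such share it is about 95%.
- **The practical loss is limited.** This partly stands. The 74% applies only if the full 30% is lost, and a true ICC slightly above 0.7, as section 5 expects, restores much of the power. But the table is built on 0.7, and at that value one pair per patient misses 90% even with no loss.
- **Later selection of the readings is speculation about conduct.** Fair. Section 8 says the data are blocked until the end of the study. The point is only that the plan leaves the choice open, and the finding on power does not depend on it.

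**Conclusion.** The concern holds. The stated 90% power at 226 was calculated for an ICC among three interchangeable readings, not for the two-device primary ICC. On the better-supported reading, one pair per patient, power is about 74% at 226 and 88% at 323, and 90% needs 348 evaluable patients. With three pooled pairs it is about 74% to 97% at 226, and the plan lacks the inputs to place it within that range. This shows that the claimed power is not established; it does not show that the trial must be underpowered.

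The figures assume that success means the lower limit of the two-sided 95% interval exceeds 0.6 (implied by the table, stated nowhere), that there is no systematic offset between devices, and that the true ICC is 0.7 except where varied. The matter should be fixed, but it does not undermine the design.

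**What to change.** 1. State which readings form the primary ICC, which ICC form is used, and the success rule.
2. If one pair per patient is primary, redo the table with k = 2. Report power of about 74% at 226 evaluable and 88% if all 323 are usable, with the sensitivity to the true ICC.
3. If all three pairs are primary, use a repeated-measures agreement model that keeps simultaneous readings paired and includes a patient-by-time term. State power over an assumed range of error correlation between repeats.
4. If the mean of three is intended, say so, and say whether 0.6 and 0.7 refer to single readings or to means.
5. If an absolute-agreement form is chosen, state the device offset assumed.

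**Cost:** a corrected table and one or two sentences. No extra patients or data are required. The drawback is that the stated power becomes lower (one pair) or conditional on an assumed correlation (three pairs).
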